8.2. Setting

Patients with HR+/HER2- ABC within the US and CAN will be enrolled from a geographically representative population as well as from diverse treatment settings (e.g., academic and community sites). ABC patients whose treatment decision with palbociclib has been made by their treating physician and meet the eligibility criteria will be invited to participate in the study. Eligibility will be assessed at the date of the enrollment visit (i.e. Baseline/Visit 1).

8.2.1. Inclusion Criteria

Patients must meet all of the following inclusion criteria to be eligible for enrollment into the study:

1. Age \geq 18 years or older.
2. Diagnosis of adenocarcinoma of the breast with evidence of metastatic disease or advanced disease not amenable to treatment with curative intent.
3. Documented HR+ (ER+ and/or PR+) tumor based on local standards.
4. Documented HER2- tumor based on local standards.
5. Physician has determined that treatment with palbociclib is indicated.
6. Evidence of a personally signed and dated informed consent document indicating that the patient has been informed of all pertinent aspects of the study.

7. Patients who in the opinion of the investigator are willing and able to comply with regular clinic visits as per standard of care practice at the site.

8.2.2. Exclusion Criteria

Patients meeting any of the following criteria will not be included in the study:

1. Patients with a life expectancy of less than 3 months at the time of ABC diagnosis, per the investigator's judgment.
2. Patients participating in any interventional clinical trial that includes investigational or marketed products at the time of enrollment. (Patients participating in other investigator initiated research or NIS can be included as long as their standard of care is not altered by the study).
3. Patients on active treatment for malignancies other than ABC at the time of enrollment.
4. Patients who are unable to understand the nature of the study and are unwilling to sign an informed consent.

Patient eligibility should be reviewed, documented, and confirmed by an appropriately qualified member of the investigator's study team before patients are enrolled in the study.

8.3. Variables

Patient demographics, study site characteristics, medical history, baseline concomitant medications, breast cancer diagnosis and recurrence history, metastatic disease status, MBC treatment, disease status and characteristics, performance status (ECOG), palbociclib dosing and treatment management, routine clinical efficacy assessment, physician MBC treatment selection survey, quality of life, geriatric screening tool and questionnaire, and **CCI** [REDACTED] will be assessed. Detailed definitions of variables that will be collected or derived for statistical analyses and summaries will be included in the Statistical Analysis Plan (SAP).

Data collected will be from the treating physicians' routine clinical assessments as per their local standard of care. Patients will be asked to complete the EORTC QLQ-C30; the G8 Geriatric Screening Tool and ADL will be completed for patients greater than or equal to 70 years of age at the time of study enrollment. The G8 Screening Tool will be completed by the treating physician or appropriately delegated site staff and the ADL will be completed by the patient or in conjunction with the appropriately delegated site staff. **CCI** [REDACTED]
[REDACTED]
[REDACTED]
[REDACTED]

The Data Entry Schedule is provided in Table 1 and the EORTC QLQ-C30 and Geriatric Assessments in Table 2.

Table 1: Data Entry Schedule

Data Collection and Entry¹	►	Baseline	During Treatment with Palbociclib	Post Treatment with Palbociclib
		SOC Visit 1	SOC Visit 2 through End of Treatment with Palbociclib	Follow-up through End of Study²
Informed Consent & Inclusion/Exclusion Criteria		x		
Patient Demographics, Study Site Characteristics, Medical History, Baseline Concomitant Medications, Baseline Metastatic Disease Status		x		
Breast Cancer Diagnosis and Recurrence History		x		
Breast Cancer Treatment ³		x ³	x ³	x ³
Physician MBC Treatment Selection Survey ⁴		x ⁴	x ⁴	x ⁴
Performance Status (ECOG)		x	x	
Clinical Assessments ⁵		x ⁵	x ⁵	x ⁵
CCI		█	█	
Laboratory: CBC ⁷		x ⁷	x ⁷	
Adverse Events and Serious Adverse Events ⁸		x ⁸	x ⁸	

SOC = Standard of care; ABC = advanced breast cancer; CBC = complete blood count; ECOG = Eastern Cooperative Oncology Group; MBC = metastatic breast cancer; SAE = serious adverse event

1. Data is collected in accordance with normal standard of care visits, enter all data available per Data Entry Schedule into the electronic data capture system.
2. Follow up through End of Study: Enter data at SOC visits where each subsequent (post palbociclib treatment) MBC treatment regimen is prescribed and at end of study.
3. Breast cancer treatment: including surgery, radiation, systemic chemotherapy, hormone therapy, and/or targeted therapy, in both neoadjuvant/adjuvant and metastatic disease settings, prior to, during, and post palbociclib treatment; supportive care is also collected in the metastatic setting while on this study.
4. Physician MBC Treatment Selection Survey: Treating physicians will complete a treating physician MBC treatment selection survey that will capture the reason(s) for treatment choice at start of palbociclib therapy and at start of subsequent therapies.
5. Clinical assessments: overall clinical response as judged by treating physician, at intervals per standard of care schedule: imaging assessment, clinical progression, and clinical biomarkers.

CCI

7. CBC: Baseline and during palbociclib treatment, enter any CBC during the 1st 3 cycles, then enter Day 1 (or prior to start of a new cycle) CBC for the subsequent cycles as per standard of care.

8. AE/SAE reporting begins at the time of the patient's first dose of palbociclib or the time of the patient's informed consent if s/he is already exposed to palbociclib and up to 28 calendar days following the last administration of palbociclib.

Table 2: EORTC QLQ-C30 and Geriatric Assessments

Data Collection and Entry	Baseline	Through End of Treatment with Palbociclib
	► SOC Visit 1	
EORTC QLQ-C30 ¹	x ¹	x ¹
G8 Screening Tool ²	x ²	x ²
ADL: Activities of Daily Living ²	x ²	x ²

ADL = Activities of Daily Living; EORTC QLQ-C30 = European Organisation for the Research and Treatment of Cancer Quality of Life Questionnaire Core 30

1. EORTC QLQ-C30 will be collected at baseline (before starting palbociclib) then monthly for the first 3 months of treatment with palbociclib, then every three months until the end of treatment with palbociclib.

2. G8 Screening Tool and Activities of Daily Living to be completed only for patients equal to or greater than 70 years of age at the time of study enrollment. G8 and ADL will be collected at baseline (before starting palbociclib) then monthly for the first 3 months of treatment with palbociclib, then every three months until the end of treatment with palbociclib. ADL to be completed by the patient or in conjunction with the appropriately delegated site staff, G8 to be completed by the treating physician or the appropriately delegated site staff.

8.4. Data Sources

All data collected in this study are intended to capture the real world treatment patterns and outcomes of patients with HR+, HER2- ABC. An electronic case report form (eCRF) will be used for data collection. The eCRF must be signed by the investigator. The signature serves to attest that the information contained on the eCRF is true. At all times, the investigator has the final responsibility for the accuracy and authenticity of all clinical and laboratory data entered into the eCRFs.

Data for this study will be obtained via the sources outlined below.

8.4.1. Patient Medical Charts

The investigator or authorized medical staff will record clinical and treatment data from patients' existing medical records into an eCRF following each patient's standard of care clinic visit.

8.4.2. Patient Questionnaires and Quality of Life

All patients enrolled in the study will be asked to participate in completing the Quality of Life instrument and Questionnaires:

- EORTC QLQ-C30 (see Annex 1 Stand Alone Documents: EORTC QLQ-C30): Collected at baseline (before starting palbociclib) then monthly for the first 3 months of treatment with palbociclib, then every three months until the end of treatment with palbociclib.
- G8 Screening Tool (see Annex 1 Stand Alone Documents: G8 Geriatric Screening Tool) and ADL (see Annex 1 Stand Alone Documents: ADL Activities of Daily Living): Collected at baseline (before starting palbociclib) then monthly for the first 3 months of treatment with palbociclib, then every three months until the end of treatment with palbociclib. ADL to be completed by the patient or in conjunction with the appropriately delegated site staff, G8 to be completed by the treating physician or the appropriately delegated site staff.

Patients can complete these assessments either on a paper form or via an electronic direct patient data capture software system.

8.4.3. Site Questionnaires

The following site questionnaires will be completed:

- Study Site Characteristics: A study site information form will be used to collect information at baseline pertaining to the practice, patient population, specialty and treatment pathways.
- Physician MBC Treatment Selection Survey: Treating physicians will also be asked to complete a treating physician MBC treatment selection survey that will capture the

reason(s) for treatment choice at start of palbociclib therapy and at start of subsequent therapies.

CCI

8.5. Study Size

This is an observational study of drug usage without any pre-defined hypothesis to be tested; rather, it addresses descriptive objectives. The estimated sample size is applied to ensure adequate exploration of the objectives and sufficient generalizability.

Power Analysis and Sample Size (PASS 13) Software (NCSS Statistical Software, 2014) was used to calculate sample size. Sample sizes are based on a range of conservative estimates for univariate statistics (hypothesis test and confidence intervals) for both dichotomous and continuous outcomes.

Dichotomous Outcomes

Hypothesis testing: A sample size of 1287 achieves 90% power to detect a difference ($P_1 - P_0$) of 0.04 using a two-sided Z test. The target significance level is 0.05. These results assume that the population proportion under the null hypothesis is 0.243 (Zar 1984; Lachin 2000; Fleiss et al, 2003; Chow 2011; Machin et al, 2011; DeSantis et al, 2014). If the null proportion is 0.163 (Tevaarwerk et al, 2013) this sample size has >90% power (Table 3).

Table 3: Sample Size for Proportion Hypothesis Test at $\alpha=0.05$

P_1-P_0	P_0	Power	N
.04	0.163	0.80	753
.04	0.163	0.85	856
.04	0.163	0.90	1004
.05	0.163	0.80	489
.05	0.163	0.85	567
.05	0.163	0.90	657
.04	0.243	0.80	955
.04	0.243	0.85	1009
.04	0.243	0.90	1287
.05	0.243	0.80	625
.05	0.243	0.85	714
.05	0.243	0.90	834

P_0 is the value of the population proportion under the null hypothesis.

P_1 is the value of the population proportion under the alternative hypothesis.

Confidence Interval: When the sample size is 1134, a two-sided 95% CI for a single proportion using the large sample normal approximation will extend 0.025 ($=0.05/2$) from the observed proportion for an expected proportion of 0.243 (Newcombe 1998; Fleiss et al, 2003; DeSantis et al, 2014). Similarly, when the sample size is 1134, a two-sided 95% CI for a single proportion using the large sample normal approximation will extend 0.029 ($=0.058/2$) from the observed proportion for an expected proportion of 0.50. This sample is adequate if the null proportion is 0.163 (Tevaarwerk et al, 2013) (Table 4).

Table 4: Sample Size 95% Confidence Interval for a Proportion at $\alpha=0.05$

CI Width	Proportion (p)	Width if $P=0.5$	N
0.05	0.163	0.068	839
0.05	0.200	0.062	984
0.05	0.243	0.058	1134
0.05	0.300	0.055	1291
0.05	0.400	0.051	1476
0.06	0.163	0.081	583
0.06	0.200	0.075	683
0.06	0.243	0.070	786
0.06	0.300	0.065	897
0.06	0.400	0.061	1025

CI = confidence interval

Continuous Outcomes

Hypothesis testing: A sample size of 1052 achieves 90% power to detect a difference of -0.30 between the null hypothesis mean of 0.00 and the alternative hypothesis mean of 0.30 with an estimated standard deviation of 3.00 and with a significance level (alpha) of 0.05 using a two-sided one-sample t-test (Zar 1984; Machin et al, 2011) (Table 5).

Table 5: Sample Size for Mean Hypothesis Test at $\alpha=0.05$

Power	Mean ₁ -Mean ₀	Standard Deviation	Effect Size	N
0.80	0.25	2.0	0.125	505
0.85	0.25	2.0	0.125	577
0.90	0.25	2.0	0.125	673
0.80	0.25	3.0	0.083	1131
0.85	0.25	3.0	0.083	1294
0.90	0.25	3.0	0.083	1514
0.80	0.30	3.0	0.100	786
0.85	0.30	3.0	0.100	899
0.90	0.30	3.0	0.100	1052
0.80	0.30	2.0	0.150	351
0.85	0.30	2.0	0.150	401
0.90	0.30	2.0	0.150	469
0.80	0.40	2.0	0.200	199
0.85	0.40	2.0	0.200	227
0.90	0.40	2.0	0.200	265
0.80	0.40	3.0	0.133	444
0.85	0.40	3.0	0.133	507
0.90	0.40	3.0	0.133	593

Confidence Interval: A sample size of 1292 produces a two-sided 95% CI with a distance from the mean to the limits that is equal to 0.30 when the estimated standard deviation is 5.5 (Hahn and Meeker 2011) (Table 6).

Table 6: Sample Size 95% Confidence Interval for a Mean at $\alpha=0.05$

Distance from the Mean ¹	Standard Deviation	N
0.1	1.5	865
0.2	3.5	1177
0.2	5.5	2906
0.3	3.5	526
0.3	5.5	1292

1. Distance from Mean to Limit is the distance from the confidence limit(s) to the mean. For two-sided intervals, it is also known as the precision, half-width, or margin of error.

The plan to enroll 1500 participants includes the expectation of increasing attrition over time. Analyses will be conducted with the data available at that time point and adjusted for missing values. This sample size is adequate to detect small effect sizes even with large amounts of variability for univariate statistics (one sample hypothesis test and CI) for both proportions and means. The sample size tables for each test or interval demonstrate sustained power to detect small to moderate effect sizes even with large amounts of attrition and show potential power at longitudinal time points with fewer observations.

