8. RESEARCH METHODS

8.1. Study Design

This is a prospective, non-interventional (NI), multicenter study being conducted in the US and CAN. The primary goal is to understand palbociclib prescribing and treatment patterns for patients with ABC being treated in routine clinical practice in the US and CAN.

Approximately 1,500 subjects will be enrolled across approximately 100 sites in the US and 10 sites in CAN. Study duration will consist of observation of patients on palbociclib treatment and approximately 3 years of follow-up post each patient's end of treatment with palbociclib, or until patient withdrawal from the study or death.

Participation in this study is not intended to change the routine treatment patients receive, as determined by their prescribing physicians; all treatment decisions, type and timing of disease monitoring are at the discretion of treating physician and patient.

Assessments include patient questionnaires and quality of life (EORTC QLQ-C30, G8 Screening Tool, ADL), site questionnaires, physician MBC treatment selection survey, and **CCI** [REDACTED], as detailed in Section 8.3 and Section 8.4.

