8 STATISTICAL ANALYSIS

This study has a convenience sample; thus, results may not be generalizable to the entire population with the disease. Due to the study's exploratory nature, study measures will be summarized descriptively. Furthermore, any p value reporting should be placed in a descriptive framework for hypothesis generation and any such inferential analysis is intended to guide further research.

All analyses will be conducted using SAS® version 9.4 or higher.

The intention is to analyze all available data. In the advent that COVID may cause gaps in subject data or require adjustments to statistical methodologies, our intent is to address such issues if or as needed. Both ICON and Pfizer have internal guidances and recommendations on file to assist with decision-making with regards to COVID-related data issues and these will be consulted if or as needed.

GENERAL METHODS

For continuous variables, means, standard deviations (SD), medians, minimums, maximums, and missing will be reported. For discrete variables, frequencies and percentages will be reported. Missing or unknown categories for each variable also will be presented. Percentages will be calculated excluding missing or unknown values. 95% Confidence Intervals (CI) are two-sided.

All summaries will be performed for all patients in the corresponding analysis set and by treatment combination defined at study entry within the corresponding analysis set:

- Palbociclib + Letrozole or Anastrozole
- Palbociclib + Fulvestrant
- Palbociclib + Exemestane
- Other

The baseline record is defined as the last observed measurement prior to palbociclib administration. Change from baseline is defined as the post-baseline value minus the baseline value.

Time in days between two dates will be calculated using the formula most recent date minus earlier date plus 1. For time in months, the same formula for days will be applied but then divided by 30.4. For time in years, the same formula for days will be applied but then divided by 365.25.

Variable definitions are found in Appendix 1 Data Derivation Details.

DISPOSITION OF SUBJECTS

A subject disposition summary will be reported. Subjects' study completion date and reason for premature termination will be reported in listing format. Number of subjects with initial diagnosis and with recurrent diagnosis will be reported in table and listing format.

DEMOGRAPHIC AND BASELINE CLINICAL CHARACTERISTICS

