8.9.1 EORTC QLQ-C30

EORTC QLQ-C30 scores and subscores will be summarized at baseline and each post-baseline visit. Paired t-test p-values will be reported. Change from baseline at each post-baseline visit will be summarized if both values are nonmissing. The EORTC QLQ-C30 scores will be compared with country population norms as part of this analysis.

Furthermore, repeated-measures models with unstructured covariance may be considered to estimate average change in global health status (as measured by the EORTC QLQ-C30) from baseline at each post-baseline timepoint. If such models will be performed, time from baseline will be included as a categorical covariate. For each outcome measure, model-based predicted values (least squares means) may be presented along with 95% CIs for each time point.

A descriptive analysis of EORTC QLQ-C30 scores and subscores will be conducted by the following categorizations: age at baseline, LOT, ECOG performance status, any dose modifications, and by SAE status. Two-sample t-test p-values will be reported for category comparisions.

PFIZER CONFIDENTIAL

In addition, differences in EORTC QLQ-C30 “worsening” (see definition in Appendix 1 Derived Data Details) percentages between categorizations for age at baseline and LOT at post-baseline timepoints. Counts and percentages will be reported along with 95% CIs (based on Wilson’s Score as Modified by Newcombe)¹⁹ and chi-square p-values.

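### Protocol 8.5 and the SAP's single-group confidence intervals assume a design effect of 1 for patients clustered in about 110 sites, so the stated precision is not assured

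*Protocol*

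**What the plan says.** **Design.** Protocol 8.1: "Approximately 1,500 subjects will be enrolled across approximately 100 sites in the US and 10 sites in CAN". The stated primary goal is to understand prescribing and treatment patterns. Treatment choice, and the kind and timing of disease monitoring, are left to the treating physician and the patient. Protocol 8.4.3 collects each practice's treatment pathways and surveys physicians on why they chose a treatment. In the SAP (Clinical Outcomes), tumor response is the physician's determination and progression is documented by the clinician.

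**Sample size.** Protocol 8.5 uses one-sample formulas.
- Interval for a proportion: "When the sample size is 1134, a two-sided 95% CI for a single proportion using the large sample normal approximation will extend 0.025".
- Test of a proportion: "A sample size of 1287 achieves 90% power to detect a difference" of 0.04, where "the population proportion under the null hypothesis is 0.243".
- Test of a mean: "A sample size of 1052 achieves 90% power to detect a difference of -0.30" with a standard deviation of 3.00.
- Interval for a mean: N = 1292 for a half-width of 0.30 at a standard deviation of 5.5.

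The only reason given for enrolling 1,500 is attrition over time.

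**Analysis.** SAP General Methods says only that "95% Confidence Intervals (CI) are two-sided". Intervals are then planned for Kaplan-Meier quartiles and survival at fixed times, for hazard ratios if Cox models are fitted, and for least squares means if repeated-measures models are fitted (8.9.1 to 8.9.3). For the EORTC worsening comparison: "Counts and percentages will be reported along with 95% CIs (based on Wilson’s Score as Modified by Newcombe". The example Cox covariates do not include site, and the repeated-measures models describe covariance across visits, with no site term. For prescribing and sequencing (Study Drug Exposure) the SAP lists counts, proportions and durations and names no interval.

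**The concern.** Patients at one site share physicians and local pathways, and their response and progression are judged by the same people. Some within-site correlation is therefore plausible for prescribing variables and for clinician-assessed outcomes. With positive correlation, the variance of a single-group estimate exceeds the independent-patient formula by the design effect, and an interval that ignores this is too narrow.

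Precision is the main yardstick of a descriptive study, and it is how protocol 8.5 justifies the sample size. Results are intended for publication, where readers would see single-group intervals whose error runs toward overconfidence by an unstated amount.

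**Working it through.** **Inputs.** N = 1500 planned; 110 sites (protocol 8.1); p = 0.243; stated Ns of 1134, 1287, 1052 and 1292 (protocol 8.5). Neither document gives an ICC or the spread of site sizes. Both are assumed below.

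**1. The plan's own figures, under independence.**
- Interval for a proportion: 1.96 × √(0.243 × 0.757 / 1134) = 0.02496, against the stated 0.025. Solving for N gives 1131, against 1134.
- Test of a proportion: [1.96 × √(0.243 × 0.757) + 1.2816 × √(0.283 × 0.717)]² / 0.04² = 1257, against 1287. Exact binomial power at 1287 with continuity correction is 0.901.
- Test of a mean at N = 1052: noncentral-t power is 0.900.
- Interval for a mean: (1.96 × 5.5 / 0.30)² rounds up to 1292.

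The plan's figures are reproduced with a design effect of 1.

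**2. Design effect (DEFF).** DEFF = 1 + (m − 1) × ICC for equal sites. Effective N = N / DEFF. The half-width is multiplied by √DEFF. Real coverage of a nominal 95% interval = 2Φ(1.96 / √DEFF) − 1.

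At N = 1500, m = 1500 / 110 = 13.64, and the half-width under independence is 0.0217:

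| Assumed ICC | DEFF | Effective N | Half-width at 0.243 | Real coverage |
|---|---|---|---|---|
| 0.02 | 1.25 | 1197 | 0.024 | 92% |
| 0.05 | 1.63 | 919 | 0.028 | 87.5% |
| 0.10 | 2.26 | 663 | 0.033 | 81% |

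At the stated N = 1134, m = 10.3. DEFF is 1.19 / 1.47 / 1.93 and the half-width is 0.027 / 0.030 / 0.035, against the stated 0.025.

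**3. How much ICC the stated figures tolerate if all 1,500 are evaluable.** The largest allowable DEFF is 1500 / (stated N), and the ICC limit is (DEFF − 1) / 12.64 for equal sites.

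| Stated figure | Largest DEFF | ICC limit |
|---|---|---|
| Proportion interval (1134) | 1.323 | 0.026 |
| Proportion test (1287) | 1.166 | 0.013 |
| Mean test (1052) | 1.426 | 0.034 |
| Mean interval (1292) | 1.161 | 0.013 |

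With unequal sites, DEFF = 1 + (m(1 + CV²) − 1) × ICC. At an assumed CV of 0.6, the limit for the proportion interval is 0.323 / (13.64 × 1.36 − 1) = 0.018. Attrition lowers these limits further.

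**4. Power, for completeness.** For 0.243 against 0.283, using the null standard error for the critical value, power at N = 1500 is 94% under independence and 89% / 80% / 66% at ICC 0.02 / 0.05 / 0.10.

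**5. Where the effect shrinks.**
- Line-of-therapy groups: if a group held half the patients (assumed), m = 6.8 and DEFF is 1.12 / 1.29 / 1.58.
- Comparisons of groups within sites: if two equal groups are present at every site and share the site effect, that effect cancels. The variance of the difference is then (1 − ICC) times the independent-patient value. At ICC 0.05, real coverage is 2Φ(1.96 / √0.95) − 1, about 95.6%, so there is no under-coverage.

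**The case against.** Four points can be made on the other side.

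**The SAP plans no interval for prescribing percentages.** A reader might infer that the intervals for the primary objective will be too narrow. The documents do not support this: the SAP names none, and its rule on two-sidedness does not create one. The precision claim for proportions sits in protocol 8.5 alone. This stands, and it confines the SAP part of the point to the intervals that are planned.

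**The stated figures may still be met.** A reader might infer that the 0.025 half-width and 90% power fail. That depends on an ICC the documents do not give; at ICC 0.02 and N = 1500 the half-width is 0.024, inside the stated 0.025. This stands too. But protocol 8.5 gives the excess over 1134 to attrition, so it is not a planned allowance for clustering.

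**Not every interval or test is affected alike.** The worsening comparisons in SAP 8.9.1 contrast age and line-of-therapy groups that can coexist within sites, so those intervals and chi-square tests need not be too narrow. This stands.

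**The study is descriptive.** Protocol 8.7 plans no formal testing and the SAP places any p-value in a hypothesis-generating frame, so lost power matters little. That is right for power but does not answer the precision point. The SAP's convenience-sample caveat concerns who was sampled, not the variance of the estimates.

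**Conclusion.** The concern holds in a limited form. Protocol 8.5 and the SAP's single-group intervals assume a design effect of 1, and nothing in either document adjusts for site. At any positive ICC, those intervals are narrower than they should be. At an assumed ICC of 0.05 with 13.6 patients per site, the interval should be about 28% wider (√1.63 = 1.28).

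The stated precision is not assured, which is less than saying it is missed. The result rests on an assumed ICC range, on equal sites unless noted, and on all 1,500 being evaluable. It applies to single-group estimates, is smaller within line-of-therapy groups, and need not apply to comparisons within sites.

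**What to change.** 1. **Protocol 8.5:** restate precision as effective N and half-width over an assumed ICC range of 0.01 to 0.10, keeping the attrition allowance separate.
2. **SAP section 8:** use site as the cluster for single-group intervals: a site-level bootstrap for Kaplan-Meier estimates, and a site random effect or empirical variance by site for the repeated-measures means. Use a robust sandwich variance by site for any Cox model.
3. **Prescribing proportions:** state that any interval published for one will be site-clustered.
4. **Reporting:** give the observed ICC for the main prescribing variables. This also describes how far prescribing varies between sites, which serves the primary goal.

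The cost is revised wording and a change of variance method, with no new data. Reported intervals would be somewhat wider and the stated precision less favourable.
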